3.2.2 Safety Endpoints

Primary safety endpoint:

Mean change in serum creatinine at 24 hours post randomization

Secondary safety endpoints:

GFR change at 24, 48, 96 hours, and at discharge (estimated from Scr)

Acute worsening of kidney function (increase in Scr 0.3 mg/dL or 25% above baseline)

Electrolyte abnormalities (hypokalemia, hypomagnesemia, hyper/hyponatremia)

Hypotension

Changes in plasma renin activity, copeptin, NT-proBNP, and cystatin C concentrations

In-hospital mortality

Hospital length of stay (ICU and total)

3.3 Study Population

3.3.1 Inclusion Criteria

- Requiring hospitalization for acute HF with signs or symptoms of volume overload (i.e. elevated JVP, rales, edema)
- Serum sodium <135 mEq/L at time of or within first 48 hours of hospitalization (A maximum of 25 patients will be enrolled with serum sodium concentrations between 130 to 134 mEq/L as the inclusion).
- Randomized within 48 hours of presentation to hospital
- ≥ 18 years of age
- Informed consent

3.3.2 Exclusion Criteria

- Severe symptomatic hyponatremia requiring acute treatment (Patients requiring intervention to raise serum sodium urgently to prevent or to treat serious neurological symptoms e.g. any seizure activity or any neurologic impairment deemed to require immediate treatment by the primary treating physician)

- Severe renal impairment upon admission (creatinine clearance < 20 mL/min)
- Renal replacement therapy dependent, or requiring upon admission
- Acute coronary syndrome on admission
- Evidence of cardiogenic shock or requiring intravenous vasopressors
- Pregnancy
- Patient requiring concomitant use of strong CYP3A4 inhibitors (clarithromycin, ketoconazole, itraconazole, ritonavir, indinavir, nelfinavir, saquinavir, nefazodone, and telithromycin)

3.3.3 Informed Consent

Signed written informed consent will be obtained prior to initiating any study procedure for each patient. A signed copy of the Right of Research Participants and the Informed Consent, will be provided to each study subject, one copy in the patient medical records, and one copy retained by the investigators.

3.4 Randomization

3.4.1 Randomization Procedure

If a patient is suitable to participate in the study and has given signed informed consent, the patient will be assigned a study number and randomized to one of the treatment arms. Randomization will occur using a computer generated randomization list prepared by the principal investigator using a 10-block scheme prior to enrollment of the first study subject. Randomization will also be stratified based on serum sodium at inclusion to 130-134 mEq/L and <130 mEq/L.

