CLINICAL PROTOCOL

**AQARESIS UTILITY FOR HYPONATREMIC ACUTE HEART FAILURE
(AQUA-AHF) STUDY**

Protocol #: HS-13-00705

Phase IV

Principal Investigators:

[name], Pharm.D.

[name].

Co-Investigators:

[name].

[name].

[name].

Study Site:

Los Angeles County + University of Southern California Medical Center

University of Southern California

Los Angeles, California

PI Contact Information:

[name], Pharm.D., FCCP, BCPS (AQ-C)

Associate Professor of Clinical Pharmacy and Medicine

University of Southern California School of Pharmacy

[name]

[name]

[contact]

[name] office

[contact] fax

Version: March 8, 2013

Amendment 1: July 30, 2014

Amendment 2: August 9, 2017

Protocol Synopsis

AQUARESIS UTILITY FOR HYPONATREMIC ACUTE HEART FAILURE (AQUA-AHF) STUDY Protocol # HS-13-00705	
Study Type	Prospective, randomized, open-label, parallel-group
Hypothesis	Volume management of acute congestive heart failure complicated by hyponatremia with a vasopressin-receptor antagonist-based aquaretic regimen is more effective and with fewer adverse events than a loop diuretic-based regimen.
Objectives	
 1. Compare urine output and length of hospital stay between a vasopressin receptor antagonist-based regimen to a loop diuretic-based regimen for hyponatremic heart failure patients hospitalized with evidence of volume overload. 2. Compare the safety (renal function, electrolyte abnormalities, and hemodynamics) of vasopressin receptor antagonist-based to a loop diuretic-based regimen for hyponatremic heart failure patients hospitalized with evidence of volume overload.

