3.4.2 Study Drugs

Study drugs (and scheduled in-patient medications) will be administered in an open-label fashion.

Patients randomized to tolvaptan will receive the study medication orally once daily. Tolvaptan tablets will be administered at 24 hour intervals, scheduled based on when the initial dose is received.

Patients randomized to furosemide will receive the medication as a continuous infusion. The loop diuretic furosemide will be prepared as per standard procedures of the hospital pharmacy for administration via continuous intravenous infusion.

After the initial 24 hour monotherapy period, escalation of the treatment regimen for either study arm will be either based on a minimum urine output < 100 mL/h or otherwise at the discretion of the primary treating physician to achieve clinical goals (e.g. relief of dyspnea, improvement in peripheral edema, resolution of jugular venous distention, improvement in pulmonary congestion based on chest radiograph, etc.). Patients randomized to furosemide will not be eligible to receive tolvaptan as a mode to treatment escalation. Tolvaptan dose will not be increased if serum sodium rises > 8 mEq/8 hours or >12 mEq/24h.

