3.5 Study Procedures

3.5.1 Screening

Patients eligible for enrollment will be screened for inclusion and exclusion criteria by one of the approved study investigators. This includes assessment and documentation of patient's past and current medical history, current admitting diagnosis, medications on admission, physical exam, and

laboratory tests. If the patient meets inclusion and exclusion criteria, signed written informed consent will be obtained. Pregnancy test will be obtained in women of childbearing age.

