6.1 Sample Size Calculation and Power Analysis

A total of 50 patients (25 in each group) would provide 93% power to detect a difference of 50% in urine output at 24 hours between treatments, $\alpha=0.05$. The power was calculated based on the magnitude of difference in urine output seen in the ACTIV-CHF²⁰ (24 hour mean urine output for tolvaptan was approximately $4100\pm 2100\text{mL}$ vs $2300\pm 1100\text{mL}$ compared to placebo when added to standard therapy) and in the Udelson et al²³ study (24 hour mean increase in urine output with tolvaptan monotherapy $2600\pm 1500\text{mL}$ vs $900\pm 850\text{mL}$ with furosemide). Based on our previous data demonstrating poor response to loop diuretics in the hyponatremia acute HF population, we believe a 50% difference (standard deviation of 25%) is a reasonable and conservative estimate of what the difference will likely be.

Amendment August 9, 2017:

Due to slow enrollment, we anticipate not achieving our desired sample size of 50 subjects. Our revised power calculation reveals that if we achieve a mean difference with the same magnitude standard deviation between groups (e.g. mean difference is $1000\pm 1000\text{mL}$), our power will be between 80-90% with a sample size between 34-46 subjects. Based on current rate of enrollment, it is likely that we will achieve a sample of at least 34 subjects, which should allow the results to be meaningful despite early termination of enrollment.

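### A single stated block size of 10 in an open-label trial with one listed site makes about 10–13% of assignments deducible by tally; a maximum-imbalance list would be a cheap improvement

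*Combined protocol and SAP*

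**What the plan says.** Section 3.4.1 describes a "computer generated randomization list prepared by the principal investigator", made "using a 10-block scheme prior to enrollment of the first study subject". It adds: "Randomization will also be stratified based on serum sodium at inclusion to 130-134 mEq/L and <130 mEq/L". Section 3.4.2 states: "Study drugs (and scheduled in-patient medications) will be administered in an open-label fashion". The title page lists one site, "Los Angeles County + University of Southern California Medical Center". Under section 3.5.1, "Patients eligible for enrollment will be screened for inclusion and exclusion criteria by one of the approved study investigators".

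Section 6.1 plans "A total of 50 patients (25 in each group"), and section 3.3.1 caps the milder stratum: "A maximum of 25 patients will be enrolled with serum sodium concentrations between 130 to 134 mEq/L". The August 2017 amendment in section 6.1 expects enrolment to stop early with at least 34 patients and works with a difference of 1000 mL and an SD of 1000 mL. Section 6.2 compares the arms with an unadjusted t-test or a non-parametric test.

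The available text mentions no second or varying block size, no withholding of the block size from those who enrol, and no allocation held centrally or by the pharmacy. Sections 8.1 and 8.2 give the pharmacy storage, records and dispensing.

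**The concern.** With one known block size and visible treatments, the list need not be seen to be partly predicted. Within a sodium stratum, once one arm has received five of the ten places, the rest of that block is certain. Before that, the arm with fewer assignments so far is the better guess. Safe custody of the list does not remove this.

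The people who screen and approach patients have assessed history, medications, examination and laboratory results by then. If an expected arm influenced whom they approached, likely good responders could collect in one arm. The difference in 24-hour urine output would then be biased, and the planned two-sample test would neither reveal nor correct it.

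**Working it through.** **Inputs.** Block of 10 and two strata (3.4.1); 1:1 allocation and N = 50 (6.1); N = 34 and SD 1000 mL (6.1, amendment). Alpha is 0.05, taken as two-sided because the plan does not say. Equal strata (25+25, 17+17) are assumed unless stated.

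**The plan's own figure.** The plan states no predictability figure. Its amended power of 80–90% at N = 34–46, with a difference equal to the SD, reproduces as 80.7% and 91.2% with a two-sided t-test. This confirms the N and SD used here.

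**Reading of the block scheme.** Ten blocks of 5 could not each be split 1:1. One block size of 10, five per arm, is the natural reading.

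**Certain assignments in a complete block.** An assignment is certain when it and all later ones in the block must go to the same arm.
- 10th: always
- 9th: 2×(5×4)/(10×9) = 44.4%
- 8th: 2×(5×4×3)/(10×9×8) = 16.7%
- 7th: 4.8%
- 6th: 0.8%
- 1st to 5th: never

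The sum is 1.67 of 10, or 16.7%. For comparison, blocks of 4 and 6 give 33% and 25%.

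**Best guess in a complete block** (Blackwell–Hodges): [5 + 0.5×(4⁵/252 − 1)]/10 = 6.53/10 = 65.3%, against 50% if unpredictable.

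**Whole trial, with incomplete last blocks.**
- 25+25: each stratum has two full blocks and five more patients, so 2×2×1.667 = 6.67 certain; 6.67/50 = 13.3%. Correct guesses 63.5%.
- 17+17: each stratum has one full block and seven more patients, so 2×(1.667 + 0.008 + 0.048) = 3.44 certain; 3.44/34 = 10.1%. Correct guesses 62.5%.
- Other splits of 34: 25+9 gives 11.8% certain and 20+14 gives 14.7%.

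**Illustration A (assumption): only certain assignments are steered, by 0.5 SD towards the expected arm.** With certain share f, the arm means move by +0.5f and −0.5f, so the bias equals f: 0.10 SD at N = 34 and 0.13 SD at N = 50. The standard error is √(4/N) SD, so the test statistic shifts by 0.101/0.343 = 0.29 and 0.133/0.283 = 0.47. Type I error is then about 6% and 7–8%; simulation agrees.

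**Illustration B (upper case): every enrolment with an untied tally is steered by 0.5 SD.** The bias is 2×0.5×(2p − 1), where p is the share of correct guesses: 2×0.625 − 1 = 0.25 SD at N = 34 and 2×0.635 − 1 = 0.27 SD at N = 50. Simulated type I error is about 9–10% and 13–14%. With 0.25 SD steering the bias is 0.13–0.14 SD and the type I error about 7%.

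**Alternatives under illustration B (simulated).**

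| List | Correct guesses | Certain | Bias (SD) | Type I error |
|---|---|---|---|---|
| Fixed block of 10 | 62–63% | 10–13% | 0.25–0.27 | about 9–14% |
| Varying blocks 8–14 | 62–63% | almost none | 0.25–0.27 | about 10–13% |
| Big-stick, limit 5 per stratum | 52–53% | 5–6% | 0.09 | about 5–6% |

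**The case against.** Stratified permuted blocks are conventional, they keep a small trial balanced, and ten is less predictable than four or six. That the size is fixed is inferred from a single number. These points stand, and they limit the size of the concern.

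A reader might infer that the published block size lets staff foresee most assignments and so pushes the type I error to 10% or more. The documents do not support that. Only about one assignment in eight to ten is certain. The larger error rates require steering at every untied enrolment, on a guess from the running arm difference that does not need the block size. They also assume a gap of 1 SD (1000 mL) between patients enrolled under opposite expectations, as large as the whole amended treatment effect. Nothing in the protocol says staff could predict response that well.

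A reader might also infer that the 48-hour window in section 3.3.1 lets staff wait for a favourable slot. Waiting helps only if another patient in the same stratum is randomized meanwhile. Assuming 34 patients over 36–48 months in equal strata, 17 patients over roughly 1,100–1,460 days gives a chance of about 2–3% in two days. Selective approach remains possible, though costly in a trial that recruits slowly.

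Finally, preparation of the list by the principal investigator, with no concealment described, is a separate and more direct weakness. Curing it would still leave the tally.

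**Conclusion.** The point holds as a modest design weakness with an inexpensive remedy. About 10–13% of assignments are deducible (16.7% in a complete block) and about 62–63% can be guessed correctly. This rests on reading the scheme as one block size of 10 with five per arm, on near-equal strata, and on someone keeping a tally by stratum.

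The consequences depend on assumed behaviour. If only deducible assignments are steered by 0.5 SD, the bias is about 100–130 mL and the type I error about 6–8%. Steering at every untied enrolment is an upper case, at about 250–270 mL and 9–14%. A reader should not infer that steering took place: the documents show opportunity only. The label is a cheap improvement.

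**What to change.** **Section 3.4.1, for assignments not yet made.** Replace the 10-block scheme with a computer-generated list per sodium stratum under a maximum-imbalance (big-stick) rule, for example limit 5. Five is the largest imbalance that a block of 10 already allows. Keep the limit out of the protocol seen by enrolling staff; this helps only if the list is also kept from them.

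Randomly varying blocks of 8–14 are a partial remedy. They remove nearly all certain assignments but leave the guess rate and the bias from tally-based guessing unchanged. Small mixed blocks (4/6/8) raise correct guesses to about 67% and should be avoided.

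**Section 6.2, for patients already randomized.** Add one sensitivity analysis of 24-hour urine output that includes each patient's allocation probability given the earlier assignments in the block. It needs only the randomization sequence. It will be imprecise at about 34 patients and should be reported as supportive.

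**Cost.** A regenerated list, one sentence in 3.4.1 and one analysis in 6.2. Mean total arm imbalance rises from about 1.7 to 3.3 patients if the rule runs throughout. At N = 34 the relative efficiency is 1 − (3.3/34)² = 0.99, so the loss of power is negligible. Since the 2017 amendment expects early termination, the new list helps only the remaining assignments, and replacing it may leave a block incomplete.

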3.4.2 Study Drugs

Study drugs (and scheduled in-patient medications) will be administered in an open-label fashion.

Patients randomized to tolvaptan will receive the study medication orally once daily. Tolvaptan tablets will be administered at 24 hour intervals, scheduled based on when the initial dose is received.

Patients randomized to furosemide will receive the medication as a continuous infusion. The loop diuretic furosemide will be prepared as per standard procedures of the hospital pharmacy for administration via continuous intravenous infusion.

After the initial 24 hour monotherapy period, escalation of the treatment regimen for either study arm will be either based on a minimum urine output < 100 mL/h or otherwise at the discretion of the primary treating physician to achieve clinical goals (e.g. relief of dyspnea, improvement in peripheral edema, resolution of jugular venous distention, improvement in pulmonary congestion based on chest radiograph, etc.). Patients randomized to furosemide will not be eligible to receive tolvaptan as a mode to treatment escalation. Tolvaptan dose will not be increased if serum sodium rises > 8 mEq/8 hours or >12 mEq/24h.

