Interventions	
 1. Tolvaptan (with rescue loop diuretic or metolazone). 2. Furosemide (with rescue metolazone) 
Eligible patients will be randomized within 48 hours of presentation to the hospital. Tolvaptan will be dosed initially at 30mg daily, with the option to titrate up to a maximum of 60mg daily. Furosemide will be initiated as a continuous infusion at 5mg/h, with the option to titrate higher. Monotherapy with the study medication must be continued for at least the first 24 hours. If after 24 hours the diuretic response is deemed inadequate, the dose of study medication may be increased and/or the use of additional diuretic agents may be initiated at the discretion of the treating physician. Physicians will be encouraged to increase the primary study drug before the use of additional diuretic agents as clinically acceptable.

Patient Population	
N=50
 
Requiring hospitalization for acute heart failure with evidence of volume overload, and a serum sodium concentration of < 135 mEq/L documented within the first 48 hours of the admission. Initial treatment with diuretics prior to randomization is allowable. A maximum of 25 patients will be enrolled with serum sodium concentrations between 130 to 134 mEq/L as the inclusion.

Inclusion Criteria	
Acute HF with signs or symptoms of volume overload (i.e. elevated JVP, rales, edema)
 
Serum sodium < 135 mEq/L at time of or within first 48 hours of hospitalization
 
Randomized within 48 hours of presentation to hospital
 
≥ 18 years of age
 
Informed consent

Exclusion Criteria
	
Severe symptomatic hyponatremia requiring acute treatment (Patients requiring intervention to raise serum sodium urgently to prevent or to treat serious neurological symptoms e.g. any seizure activity or any neurologic impairment deemed to require immediate treatment by the primary treating physician) Severe renal impairment upon admission (creatinine clearance < 20 mL/min) Renal replacement therapy dependent, or requiring upon admission Acute coronary syndrome on admission Evidence of cardiogenic shock or requiring intravenous vasopressors VAD Pregnancy Patient requiring concomitant use of strong CYP3A4 inhibitors (clarithromycin, ketoconazole, itraconazole, ritonavir, indinavir, nelfinavir, saquinavir, nefazodone, and telithromycin)

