3.2 Study Endpoints

3.2.1 Efficacy Endpoints

Primary efficacy endpoint:

Mean urine output at 24 hours post randomization

Secondary efficacy endpoints:

Urine output at 8, 48, 96 hours post-randomization, total at discharge

Mean hourly urine output at 24 hours

Serum sodium change at 8, 24, 48, 96 hours, and at discharge

Weight change at 24, 48, 96 hours, and at discharge

Cumulative furosemide dose at 48, 96 hours, and at discharge

Cumulative use of metolazone at 48, 96 hours, and at discharge

Change in self-rated dyspnea (Likert Scale) at 24 and 96 hours

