4.1 Data Points

	Randomization	8 hours	24 hours	48 hours	72 hours	96 hours	Discharge
Vital Statistics	X	X	X	X	X	X	X
UO (Fluid Balance)	X	X	X	X	X	X	X
Weight	X		X	X	X	X	X
Serum Chemistries	X	X	X	X	X	X	X
Cystatin C	X		X			X	
PRA	X		X			X	

Copeptin	X		X			X	
NT-proBNP	X		X			X	

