5.1 Definitions

Acute worsening of kidney function will be defined as an increase in Scr of 0.3 mg/dL or 25% above baseline (Scr at time of randomization).

Electrolyte abnormalities will be defined as an occurrence of a laboratory value beyond the upper or lower limit of normal as defined by the institution's laboratory standards (hypokalemia $K^+ < 3.5$ mEq/L, hypomagnesemia $Mg^{2+} < 1.7$ mEq/L, hypernatremia $Na^+ > 145$ mEq/L)

Serum sodium overcorrection will be defined as the occurrence of an increase in serum $Na^+ > 8$ mEq/L in 8 hours or > 12 mEq/L in 24 hours. For each event, any new neurologic sequelae (dysarthria, mutism, dysphagia, lethargy, affective changes, spastic quadriparesis, seizures, coma and death) of overcorrection will also be recorded, otherwise the subject will be noted to be asymptomatic.

Hypotension will be defined as a systolic blood pressure reading < 80 mmHg (confirmed by immediate repeat assessment) or a systolic blood pressure < 90 mmHg with symptoms.

In-hospital mortality will be defined as any study subject death during the hospitalization regardless of cause.

Safety Information will be collected in accordance with the current Code of Federal Regulations.

Safety information is defined as “Any information from any source containing information” such as:

- Adverse event or suspicion thereof
- Lack of efficacy
- Overdose, abuse, misuse (even without resulting adverse reaction)
- Medication error
- Exposure during pregnancy or lactation (including uneventful) and reports where the embryo or fetus may have been exposed to medicinal products (either through maternal exposure or transmission of a medicinal product via semen following paternal exposure)
- Counterfeit product
- Transfer of infectious disease by the medicinal product concerned
- Product complaint report which includes medically important information
- Pediatric use
- Occupational exposure
- Off-label use

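### The 8-hour sodium-rise limit can be measured on the scheduled draws only at 0-8 h, so a breach after a tolvaptan increase can go undetected; dosing after a detected breach is left to general discretion

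*Combined protocol and SAP*

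**What the plan says.** Section 3.4.2 (Study Drugs) sets a sodium limit on raising tolvaptan: "Tolvaptan dose will not be increased if serum sodium rises > 8 mEq/8 hours or >12 mEq/24h". It also fixes the dosing interval: "Tolvaptan tablets will be administered at 24 hour intervals, scheduled based on when the initial dose is received". Escalation in either arm is possible only once the first 24 hours of monotherapy are over.

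Section 5.1 (Definitions) applies the same limits to an adverse event: "Serum sodium overcorrection will be defined as the occurrence of an increase in serum $Na^+ > 8$ mEq/L in 8 hours or > 12 mEq/L" over 24 hours. The stated action is to note any new neurologic sequelae "of overcorrection will also be recorded, otherwise the subject will be noted to be asymptomatic".

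The row "Serum Chemistries" in 4.1, the labs row in 3.1.2 and the visit lists in 3.5 agree on when sodium is measured: randomization, 8, 24, 48, 72 and 96 h, and discharge. The visits at 24, 48, 72 and 96 h also allow the regimen to be continued or adjusted. Section 3.6 lets the treating physician or principal investigators take a patient off the study protocol at any time on safety grounds. It names no sodium criterion.

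**The concern.** A limit stated per 8 hours needs sodium values about 8 hours apart. After the 8-hour draw the next is 16 hours later, and from 24 h the scheduled draws are 24 hours apart. A higher tolvaptan dose can be given only in that later period, so half of the rule cannot be checked on the required draws once the dose has been raised.

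Two things are at stake. First, this is the only sodium-based dosing rule in the protocol, and a site that follows the plan exactly can miss a breach of one of its two limits. Second, the trial's hypothesis includes fewer adverse events with the vasopressin-antagonist regimen, and section 2 describes tolvaptan as effective at raising sodium. Uncaptured 8-hour rises would plausibly fall more in the tolvaptan arm, although the documents give no figure for how often that would happen.

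A separate, smaller gap concerns what follows a breach that is detected. No sentence ties the overcorrection definition to the next scheduled dose.

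**Working it through.** The plan gives no figure on this point to reproduce. The check is a count of measurable windows.

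**Inputs**
- Limits: a rise of more than 8 mEq in 8 h, or more than 12 mEq in 24 h (3.4.2, 5.1).
- Scheduled sodium times to 96 h: t = {0, 8, 24, 48, 72, 96} (3.1.2, 3.5, 4.1).
- First permitted increase: after 24 h (synopsis, 3.4.2).
- Listed points for adjusting treatment: 24, 48, 72 and 96 h (3.5.4 to 3.5.7).

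**Step 1: windows with a scheduled draw at both ends.** A window from s to s + w is measurable if both ends are in t.

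| Limit | Consecutive windows to 96 h | Measurable | From 24 h on |
|---|---|---|---|
| 8 h | 96 / 8 = 12 | 1 (0-8 h), 1/12 = 8% | (96 - 24) / 8 = 9 windows, 0 measurable |
| 24 h | 96 / 24 = 4 | 4 (0-24, 24-48, 48-72, 72-96 h) | 3 windows, 3 measurable |

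**Step 2: what can be checked at each decision time d.** For the 24-hour limit, d - 24 = 0, 24, 48, 72, all in t. For the 8-hour limit, d - 8 = 16, 40, 64, 88, none in t.

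**Step 3: what widely spaced draws can still prove.** Over a gap of 8k hours, at least one of the k successive 8-hour segments must exceed 8 mEq/L only if the net rise exceeds 8k.
- 8-24 h: k = 2, so the net rise must exceed 16 mEq/L.
- Any 24-hour gap: k = 3, so the net rise must exceed 24 mEq/L.

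A net rise above 12 over either gap already meets the 24-hour limit. The breaches that can be missed are therefore those in which sodium rises by more than 8 within 8 hours while the change between scheduled draws stays at 12 or below.

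**Step 4: illustration with assumed values.** Take changes from baseline of +0 at 8 h, +9 at 16 h and +11 at 24 h. The rise from 8 to 16 h is 9, which exceeds 8. The scheduled draws show 0 over 0-8 h and 11 over 0-24 h, so neither limit is met. The same pattern placed after an increase at 24 h (+0 at 24 h, +9 at 32 h, +11 at 48 h) shows a change of 11 over 24-48 h and is missed in the same way. This shows that a miss is possible, not how often it occurs.

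**Step 5: the stated consequences side by side.**
- 3.4.2: the dose is not raised; tablets remain due every 24 hours.
- 5.1: the event and any sequelae are recorded.
- 3.5: the regimen may be adjusted at 24, 48, 72 and 96 h; no criterion is given.
- 3.6: removal at the clinicians' discretion; sodium is not mentioned.

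**The case against.** The best reply is that the plan is safer than a count of 8-hour windows suggests. Much of it stands.

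- A reader might infer that the sodium limit as a whole mostly cannot be assessed. The documents do not support that: the 24-hour limit can be checked at every listed decision point to 96 h.
- A reader might infer that the rule does nothing in the first 24 hours. In fact the 0-8 h and 0-24 h values are available at the first decision on an increase and can block it.
- A reader might see a conflict with the synopsis sentence "Monotherapy with the study medication must be continued for at least the first 24 hours". Tolvaptan is given once daily, so the second tablet falls due as that period ends. Read in context, the sentence restricts add-on agents and early escalation, and it does not compel a further dose.
- A reader might conclude that most qualifying rises are missed. A share of clock windows is not a share of events, and the documents give no time course of sodium. Section 5.1 defines the event by occurrence rather than by visit, and 5.2 describes continuous monitoring that includes laboratory work-up, so unscheduled values could capture some rises.
- Handling after a breach is discretionary under 3.5 and 3.6. That is a gap in specificity, not a contradiction. Overcorrection is also not named among the safety endpoints in 3.2.2, and neither primary endpoint is affected.

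What the reply does not answer is the 8-hour limit after 8 h. No section requires extra sodium values or says that they feed the rule, and discretion cannot act on a rise that no required draw captures.

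**Conclusion.** The point holds for the 8-hour limit. On the required schedule it is measurable in 1 of 12 consecutive windows to 96 h and in 0 of 9 from 24 h, when increases are first allowed. An 8-hour breach after an increase can go undetected, and overcorrection events may be undercounted by an unknown amount. The 24-hour limit is not affected up to 96 h. In addition, the documents attach no sodium-specific instruction on the next dose to a patient who meets the 5.1 definition.

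This rests on three assumptions:
- The schedule is taken as the minimum that sites must do. Routine extra draws would narrow the gap, but the plan does not call for them.
- Windows are aligned with the draws. A 24-hour window starting between draws is not measured, and after 96 h nothing is scheduled until discharge. The efficacy list ("Serum sodium change at 8, 24, 48, 96 hours, and at discharge") omits 72 h, but the laboratory schedule includes it.
- Visit times follow randomization and tablets follow the first dose. If the two clocks differ, even the 0-8 h pair may not match the first 8 hours on drug.

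**What to change.** 1. Reconcile 3.4.2 and 5.1 with the schedule in 3.1.2, 3.5 and 4.1. Either time serum sodium draws so that they bracket the window the rule uses, including after a tolvaptan increase, or restate both the rule and the overcorrection definition in windows the schedule measures. State whether unscheduled sodium values count towards either.
2. Reconcile 3.4.2, 5.1 and 3.6 on how a patient who meets the overcorrection definition is handled when the next dose is due. The clinical content is for the investigators to decide.
3. When overcorrection is reported, give the draw times on which it was assessed, so that a reader can see which 8-hour windows were observed.

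Restating the rule costs wording only. Changing the schedule adds at most a few sodium values, and slightly more blood sampling, in inpatients whose chemistries are already being drawn.
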